2.3.1 Efficacy populations

The primary efficacy analysis will be performed on the all-treated population.

The response evaluable population will be used for sensitivity efficacy analyses of the BOR and the DCR.

2.3.1.1 All treated population

The all-treated population (AT) consists of enrolled patients who will actually receive at least one dose or any partial of a dose of study treatment.

2.3.1.2 Response evaluable population

The response evaluable population will be defined as the patients of the all treated population with measurable disease at study entry and with CA6 positivity according to the threshold defined in the relevant study part (Part 1 and Part 2a or Part 2b) and who had an evaluable response assessment during treatment (until 30 days after last SAR566658 administration). Treated patients who could not have a postbaseline tumor assessment because of early disease progression or early death due to progressive disease are also included in the response evaluable population.

An evaluable response assessment is defined as a response assessment with a response different of NE.

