1.2 STUDY FLOW CHART

Day	Prescreening ^a	Screening (prior to first infusion) ^b		R A N D O M I Z A T I O N ^c	Treatment Cycle 1					Treatment Cycle 2				Subsequent cycles			End of treatment (Day 30 after last infusion)	Follow-up period ^l
		-21 to 1	-7 to 1		-1	1 ^d	8 ^d	15	21	1 ^d	8 ^d	15	21	1 ^d	8 ^d	21		
CA6 expression status (archival tumor tissue) – central IHC/ prescreening Informed consent	X																	
Inclusion/exclusion criteria/ Informed Consent		X																
Demography and medical/disease history		X																
Physical examination ^{e/} signs and symptoms			X				X	X	X		X	X	X		X	X	X	X
Hematology ^f			X				X	X	X		X	X	X		X	X	X	
Coagulation ^g			X					X			X				X		X	
Blood chemistry ^h			X				X	X	X		X	X	X		X		X	
Serum pregnancy test ⁱ			X						X				X				X	
12-lead ECG ^j			X														X	
SAR56658 administration ^k						X	X			X	X			X	X			
Primary prophylaxis for ocular event ^l						X	X			X	X			X	X			
Hospitalization ^m					X	X												
AE assessment ⁿ		Continuously throughout the study period																
Concomitant medication ^o		Continuously throughout the study period																
PK/immunogenicity assessment ^p		See PK/immunogenicity flow chart																
Specific ocular tests ^q		X																
Tumor assessment ^r		X											X				X	X

Day	Prescreening ^a	Screening (prior to first infusion) ^b		Treatment Cycle 1					Treatment Cycle 2				Subsequent cycles			End of treatment (Day 30 after last infusion)	Follow-up period ^t
		-21 to 1	-7 to 1	-1	1 ^d	8 ^d	15	21	1 ^d	8 ^d	15	21	1 ^d	8 ^d	21		
Circulating CA6 ^s					X												
██████████					X				X				X			X	X
██████ ██████					X											X	
██████████ ██████					X												
Further anticancer therapy																	X
Survival status ^u																	X

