- e **Physical examination** will include: examination of major body systems, height (at baseline only), body weight, ECOG PS, and vital signs (temperature, blood pressure). At the follow-up visit, only ECOG PS and weight will be collected. Signs and symptoms will be reported in the eCRF as AEs only if they are still present at the time of first IMP administration.
- f **Hematology:** hemoglobin, WBC with differential, platelet counts. These tests will be done weekly for Cycles 1 and 2. If Grade 4 neutropenia occurs, assess ANC every 2-3 days until ANC $\geq 0.5 \times 10^9/L$.
- g **Coagulation:** INR.
- h **Blood chemistry:** liver function tests: AST, ALT, total bilirubin, conjugated bilirubin, AP, electrolytes: sodium, potassium, calcium, phosphate, and chloride. Renal function tests: creatinine and BUN or urea. Others: glucose, LDH, albumin, and total proteins. These tests will be done weekly during the 2 first cycles then every 3 weeks for subsequent cycles, except for BUN and chloride that will be done weekly only during the first cycle. Additional tests will be performed when clinically appropriate. In case of Grade ≥ 3 liver function abnormal tests, additional tests will be done every 2 to 3 days until recovery to baseline value.
- i **Serum pregnancy test:** women of child-bearing potential must have a negative serum pregnancy test result within 7 days prior to the initial dose of IMP and at the end of treatment evaluation (between D22 and D30 after the last IMP administration). The serum pregnancy test will also be performed before each cycle, only in countries where it is a regulatory requirement.
- j **12-lead ECG** is required at baseline and at end of treatment. To be repeated as clinically indicated.

- k* **SAR566658 administration:** on Day 1 and Day 8 of each treatment cycle, the patient's BSA will be determined using the current weight and baseline height. For patients with a BSA >2.0 m², the dose will be calculated on the basis of 2.0 m² BSA. Premedication with histamine H1 antagonist is required: diphenhydramine 50 mg given orally approximately 1 hour before SAR566658 administration.

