- q* **Specific complete ocular examination** at baseline will include: assessment of ocular/visual symptoms, visual acuity, full ocular tests including slit lamp with fluorescein under dilatation, and Schirmer's test preferably with anesthetics. In patients with any ocular/visual symptom(s) (eg, blurred vision, photophobia) the complete ocular tests will be repeated at the time of the occurrence of the ocular toxicity. Then, visual acuity, slit lamp examination under dilatation, and Schirmer's test will be repeated once weekly until resolution to Grade 1. In case of recurrent ocular toxicity observed in subsequent cycles, visual acuity and slit lamp examination with fluorescein under dilatation, and Schirmer's test preferably with anesthetics will be performed at the time of the event onset, then weekly until resolution to Grade 1. Moreover, tonometry will be performed at screening, at the end of Cycle 6 (with a time window of 4 days preceding the following cycle administration), whenever clinically indicated, and at End of Treatment, to assess and monitor intraocular pressure. At screening, tonometry will be performed with and without dilation, and only without dilation at the subsequent time points.
- r* **Tumor assessment** as per RECIST1.1: CT-scan or MRI and any other examinations as clinically indicated will be performed to assess disease status at baseline, every 6 weeks during the study treatment period until radiological disease progression or study cut-off, whichever comes first, and at the end of study treatment, except if already done at last cycle. Confirmatory radiological evaluation will be performed at least 4 weeks after initial documentation of response.
- s* [REDACTED]

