10.1.5 End of treatment

All patients must continue to be observed for at least 30 days after the final dose of study treatment. The following procedures should be performed between 25 and 35 days after the last SAR566658 administration:

- **Physical examination** including major body systems examination, body weight, ECOG PS, and vital signs (temperature and blood pressure).
- **Concomitant medications.**
- **Adverse events.**
- **Tonometry** (without dilatation) to measure intraocular pressure.
- **Hematology:** WBC with differential count, hemoglobin, platelet count.

- **Blood Chemistry:** sodium, potassium, calcium, phosphate, chloride, creatinine, creatinine clearance if creatinine >1.5 x ULN, BUN or urea, AST, ALT, total bilirubin, conjugated bilirubin, alkaline phosphatase, glucose, LDH, albumin, and total protein.
- **Coagulation tests:** INR.
- **Serum pregnancy test** for women of child-bearing potential.
- **12-lead ECG.**
- [REDACTED]
- [REDACTED]
- **Blood sampling for PK:** as specified in PK/immunogenicity flow chart (see [Section 1.4](#)).
- **Blood sampling for ATA:** as specified in PK/immunogenicity flow chart (see [Section 1.4](#)).
- **Tumor assessment:** (abdominal/chest) CT scan or MRI, and all other exams as clinically indicated (eg, brain CT scan or MRI in case of clinical suspicion of central nervous system involvement) to assess all TARGET or NON TARGET lesions. To ensure comparability, the imaging should be performed using identical techniques throughout the study period (ie, scans performed immediately following bolus contrast administration using a standard volume of contrast, the identical contrast agent, and preferably the same scanner).
Confirmation of objective responses will be performed by repeat tumor imaging (CT scan, MRI) at least 4 weeks after the first radiological documentation of response (see [Section 9.1.2](#)).
- **Other investigations** if clinically indicated.

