2.1.3 Efficacy endpoints

2.1.3.1 Primary efficacy endpoint(s)

The primary efficacy endpoint will be the Overall Response Rate (ORR) defined as the proportion of patients with confirmed complete response (CR) or confirmed partial response (PR) as Best

Overall Response (BOR), assessed by the Investigator (based on RECIST 1.1), relative to the total number of patients in the efficacy population (see [Section 2.3.1](#)). Confirmation of objective responses will be performed by repeat tumor imaging (Computed Tomography [CT] scan, MRI) at least 4 weeks after the first radiological documentation of response.

Tumor assessments will be performed every 6 weeks (ie, every 2 cycles) during the treatment period and every 6 weeks during the follow-up period if a patient discontinues treatment prior to radiologic disease progression.

Tumor assessments after the initiation of post-treatment anti-cancer therapy will be excluded from the determination of Best Overall Response in a patient. See [Appendix B](#) (Determination of tumor response) for details.

Best Overall Response

BOR is the best tumor response observed from first study treatment infusion until disease progression, death or initiation of post-treatment anti-cancer therapy, whichever occurs first.

Primary ORR analysis can be performed when all patients treated in Part 2a and Part 2b have had at least 4 postbaseline tumor assessments, experienced confirmed objective response, or have discontinued the study for any reason. However, if the primary criteria of 7 responders is either met or not met with certainty at the end of the Part 2a in the selected dose when all patients have had 2 postbaseline tumor assessments, experienced confirmed objective response, or discontinued the study for any reason and when all the patients of the Part 2b have had 2 postbaseline tumor assessments, experienced confirmed objective response, or discontinued the study for any reason, analysis may be done at that time instead.

Best tumor shrinkage

For patients with measurable disease, the best tumor shrinkage will be defined by the best relative change from baseline as follows:

$$Y = 100 \times \frac{Y_{smallest} - Y_{baseline}}{Y_{baseline}}$$

Where Y is the sum of longest diameter of the target lesions.

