2.1.4 Safety endpoints

The safety analysis will be based on the reported adverse events (AE) and other safety information, such as clinical laboratory data, vital signs, ECG, weight and Eastern Cooperative Oncology Group (ECOG) performance status (PS).

Observation period

The observation period will be divided into 3 periods:

- The **pre-treatment** period is defined as the time from the signed informed consent date up to the first study treatment administration.
- The **treatment** period is defined as the time from the first study treatment administration to the last study treatment administration + 30 days.
- The **post-treatment** period is defined as the period of time starting the day after the end of the treatment period up to the end of the study.

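### A protocol-compliant end-of-treatment scan on Days 31 to 35 after the last dose cannot make a patient response evaluable, and laboratory values from those days miss the on-treatment grade table

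*SAP*

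**What the plan says.** Protocol 10.1.5 sets the window for the end-of-treatment visit: "The following procedures should be performed between 25 and 35 days after the last SAR566658 administration". The listed procedures include the tumor scan, hematology, chemistry, INR, weight and vital signs.

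Two other places time the same visit differently. The flow chart in Protocol 1.2 has "End of treatment (Day 30 after last infusion"). Footnote i in Protocol 1.3, on the pregnancy test, has "between D22 and D30 after the last IMP administration". Footnote r asks for a scan during treatment every 6 weeks "and at the end of study treatment, except if already done at last cycle".

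The analysis windows close earlier. In SAP 2.1.4 (as in Protocol 11.4.5.1) the treatment "period is defined as the time from the first study treatment administration to the last study treatment administration + 30 days". SAP 2.3.1.2 and Protocol 11.3.3 admit to the response evaluable population patients "who had an evaluable response assessment during treatment (until 30 days after last SAR566658 administration"). Both also admit treated patients who had no post-baseline scan because of early progression or early death from it.

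The response itself has no such limit. SAP 2.1.3.1 states that "BOR is the best tumor response observed from first study treatment infusion until disease progression, death or initiation of post-treatment anti-cancer therapy", whichever comes first. The primary ORR uses all treated patients (SAP 2.3.1 and 2.4.4.1). The response evaluable population serves the sensitivity analyses of ORR and DCR (SAP 2.4.4.1 and 2.4.4.2.1).

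**The concern.** A site can follow Protocol 10.1.5 to the letter and still produce a scan that the SAP does not accept as qualifying. The carve-in covers progression and progression-related death only. A patient who stops in Cycle 1 for toxicity or by choice, and is then scanned on schedule, has no such protection. That patient could even be a confirmed responder in the primary analysis while not being response evaluable, because BOR runs past Day 30.

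The same cut affects safety tables. SAP 2.4.5.4 summarizes laboratory grades during treatment, and SAP 2.4.5.5 counts PCSAs for blood pressure and weight in the treatment-emergent period. No laboratory-grade or PCSA table is specified for the post-treatment period, so compliant values from Days 31 to 35 have no assigned place in either summary.

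At stake are the composition of the sole sensitivity population for the primary endpoint, and the completeness of the tables at the one scheduled safety visit after treatment.

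**Working it through.** **1. The plan's own figure.** Inputs (SAP 1.3.2 and 3): 14 then 15 patients; stop at 0 or 1 response in 14; reject at 6 or more of 14, or at 7 or more of 29; H0 12%, H1 30%.

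P(reject | p) = P(X1 ≥ 6) + Σ over x = 2 to 5 of P(X1 = x) · P(X2 ≥ 7 − x), with X1 ~ Bin(14, p) and X2 ~ Bin(15, p).

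- p = 0.30: 0.800, against a stated power of 80%.
- p = 0.12: 0.050, within the stated 10% ceiling.

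The power is reproduced. The rule is applied to all treated patients, so the Day 30 limit does not enter it.

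**2. Overlap of the windows.** Days 25 to 35 are 35 − 25 + 1 = 11 days. Days 31 to 35 are 5 days, all past the limit. This is a share of permitted days (5/11 = 45%), not of visits or patients.

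**3. Who can be affected.** Scans fall every 6 weeks after the first dose, so with the first dose on Day 1 the first scan is on about Day 43.

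| Last dose | Study day | Limit (+30) | Visit window (+25 to +35) | Day 43 scan, days after last dose |
|---|---|---|---|---|
| Cycle 1 Day 1 | 1 | 31 | 26 to 36 | 42: past the limit |
| Cycle 1 Day 8 | 8 | 38 | 33 to 43 | 35: in the visit window, past the limit |
| Cycle 2 Day 1 | 22 | 52 | 47 to 57 | 21: inside the limit |
| Cycle 2 Day 8 | 29 | 59 | 54 to 64 | 14: inside the limit |

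On the nominal schedule, then, only patients dosed in Cycle 1 alone can be lost, and only if they stopped for a reason outside the carve-in and had no evaluable scan by Day 30. For a patient dosed only on Day 1 there is a further snag. SAP Appendix B does not accept stable disease less than 35 days from first dose, so no scan inside the Day 31 limit can establish it.

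**4. Effect on the sensitivity ORR.** The documents give no number of affected patients; 0 to 3 is an assumption. Start from 7 responders in 29 and use Clopper-Pearson 80% intervals, as in SAP 2.4.4.1.

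| Patients lost | ORR | 80% CI |
|---|---|---|
| none | 7/29 = 24.1% | 14.0 to 37.2 |
| 1 non-responder | 7/28 = 25.0% | 14.5 to 38.5 |
| 2 non-responders | 7/27 = 25.9% | 15.1 to 39.7 |
| 3 non-responders | 7/26 = 26.9% | 15.7 to 41.1 |
| 1 responder | 6/28 = 21.4% | 11.7 to 34.6 |
| 1 responder and 2 non-responders | 6/26 = 23.1% | 12.6 to 37.0 |

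Each lost non-responder adds about one percentage point. A lost responder moves the rate the other way.

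**The case against.** The strongest reply is that little follows from the mismatch. Much of that stands.

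- A reader might infer that scans on Days 31 to 35 are thrown away. They are not. BOR, the primary ORR, DOR, TTP and PFS have no Day 30 limit. Such a scan fails only as the qualifying scan for one sensitivity population.
- A reader might infer that early stoppers as a group drop out. Early progression and progression-related death are kept in, as is anyone with an earlier evaluable scan. Patients dosed in Cycle 2 have the 6-week scan well inside the limit. The flow chart's nominal Day 30 visit is also inside it: study Day 38 after a last dose on Day 8.
- On safety, ECG is summarized at the end-of-treatment visit (SAP 2.4.5.6), pregnancy tests over the whole study (SAP 2.4.5.4), and post-treatment adverse events in their own tables (SAP 2.4.5.1). The table of last and worst blood pressures states no Day 30 limit. SAP 2.1.4.4 assigns laboratory values to cycles without a Day 30 cut, and SAP 2.5.5 leaves room for windows on laboratory and vital-sign data.
- An on-treatment evaluable set can be a deliberate contrast to the all-treated analysis.

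Two things remain. Even a deliberate on-treatment set should not turn on which permitted day the visit takes place. And optional windows that are not defined do not settle where a Day 33 laboratory value goes when the grade table is restricted to treatment and the treatment period ends at Day 30.

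**Conclusion.** The point holds and is minor. Protocol 10.1.5 and the Day 30 limit contradict each other on 5 of 11 permitted days. Followed exactly, the plan can exclude an on-schedule patient from the only specified sensitivity analysis of the primary endpoint. It also leaves compliant laboratory, blood pressure and weight values outside the grade and PCSA tables.

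The primary test is unaffected. The range of 25.0% to 26.9%, against 24.1%, rests on an assumed loss of 1 to 3 non-responders from a result of 7/29. A reader might conclude that the sensitivity ORR is biased upward, or more so at the higher dose. The documents do not support either: they give no count of affected patients, no response rate among them and no split by dose, and the rate falls if a responder is lost.

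**What to change.** 1. In Protocol 11.3.3 and SAP 2.3.1.2, let an evaluable assessment at the protocol-defined end-of-treatment visit (up to last dose + 35 days under 10.1.5) confer response evaluable status. Alternatively, accept any valid post-baseline assessment before post-treatment anticancer therapy, which is the window BOR already uses. The first option is enough to remove the mismatch; the second also covers the Day 43 scan of a patient dosed only on Day 1.
2. In SAP 2.1.4, assign laboratory and vital-sign results from the end-of-treatment visit (up to Day 35) to the on-treatment summaries, including the PCSA table. Leave the definition of treatment-emergent adverse events at 30 days. ECG needs no change.
3. Reconcile the end-of-treatment timings in the flow chart, footnote i and Protocol 10.1.5, and carry the agreed window into items 1 and 2.

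The cost is wording in both documents and one programming flag. The downside is that a few values collected up to 5 days later count as on-treatment. The change should be made before the data are seen, because deciding afterwards who is evaluable would weaken the sensitivity analysis.

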2.3.2 Safety population

The population used for safety analyses consists of the all-treated population. Any safety analysis will be performed on this population

2.3.3 Evaluable for predefined safety criteria population (Part 1)

Patients evaluable for predefined selection criteria will be defined as patients treated who have completed 2 cycles or who experienced predefined safety criteria. To complete 2 cycles, patients have to receive 4 infusions and more than 80% of the cumulative planned dose. This population is only defined for Part 1 for the purpose of the Bayesian design and the analysis of the predefined safety criteria.

2.3.4 Pharmacokinetic population

The PK population will include all patients who received at least 1 dose of SAR566658, even if incomplete, and have at least 1 valid PK parameter available.

2.3.5 Evaluable population for immunogenicity

The evaluable population for immunogenicity will include all patients with at least 1 sample drawn postbaseline after study drug infusion (on-treatment period or follow-up) that is appropriate for ATA testing with a reportable result (patients with missing ATA at baseline will be considered evaluable).

2.4 STATISTICAL METHODS

Continuous data will be summarized using the number of available data, mean, standard deviation, median, minimum, Q1, Q3 and maximum. Categorical and ordinal data will be summarized using the number and percentage of patients.

All the tables will be presented by the intended dose level in the Part 1 and by actual expression cohort at the selected dose in the Part 2 (mild expression or overexpression cohorts). Separate tables will be provided for Part 1 and Part 2. Summary table including both dose levels and expression cohorts will be provided for some analyses as demographics or analysis population topics.

2.4.1 Demographics and baseline characteristics

The parameters described in [Section 2.1.1](#) will be summarized on the all-treated population analyzed in the planned dose level using descriptive statistics.

The medical and surgical history will be summarized according to the SOC and PT. Separate tables will summarize ocular history, peripheral neuropathy history.

For the safety parameters, the baseline values will be described along with each safety analysis if relevant.

2.4.2 Prior, concomitant and post treatment medications (other than anticancer therapies)

The prior, concomitant and post-treatment medications will be presented for the all-treated population.

Medications will be summarized according to the WHO-DD dictionary, considering the first digit of the anatomic category (ATC) class (anatomic category) and the first 3 digits of the ATC class (therapeutic category). All ATC codes corresponding to a medication will be summarized, and patients will be counted once in each ATC category (anatomic or therapeutic) linked to the medication. Therefore patients may be counted several times for the same medication.

The table for prior medications will be sorted by decreasing frequency of ATC followed by all other therapeutic classes. In case of equal frequency regarding ATCs alphabetical order will be used. In part 1, sorting will be based on results for the dose level 120 mg/m² D1D8 Q3w and in part 2, sorting will be based on the All column including overexpression and mild expression cohorts at the selected dose.

The tables for concomitant and posttreatment medications will be sorted in the same way.

Premedications

Number (%) of patients compliant with premedications for ocular toxicities as defined in [Section 2.1.2](#) will be provided.

Compliance will be calculated for each administered infusion. It will be a binary variable, patient will be considered as compliant or as not compliant for the whole infusion. Total compliance will be calculated as the mean compliance over all administered infusions.

